This study is a single-center, simple random parallel group design clinical trial, each random group is allocated according to the proportion of 1:1:1.

IV. Clinical trial site

Responsibilities: Second Affiliated Hospital of Zhejiang University; [name];
[contact];

Address: [name]
Province; [name]

Participation Unit: the Second Affiliated Hospital of Zhejiang University Medical College; person in charge: [name]

V. Design of research

1. Inclusion criteria

(1) Age 18-80 years old; (2) a teeth choice: 6-8 weeks after the teeth after the periodic treatment of teeth, there is at least one site periodontal diagnosis depth (PD) ≥ 5 mm, looseness is less than II The degree or II-III degree will be loose after a fixed fixed, imaging evaluation of the vertical bone absorption of the teeth is greater than 3 mm osteogenesis, and the site is free of teeth surgical treatment, the patient has no obvious symptoms; (3) Patients have better compliance, and the bacterial plaque control is good after the basic treatment (all-in-law bleeding index and the mushroom index), can understand the purpose of testing, willing to cooperate with surgery and follow-up, voluntarily participate in the test and signed Informed consent.

2. Exclusion criteria

(1) In the past 6 months, chewing smokeless tobacco, smoking or suction cigar once a week or more, or smoking more than 20 / week (1 pack / week); (2) patients before blood Three months taking any drug or platelet counts that affect platelet function less than 200,000 / mm³; (3) patients have taken anti-epileptic drugs, antiplasia, antidepressants, sedatives, califiers, anti-depression, sedatives in the

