first 1 month before surgery Inflammatory drug or daily analgesic; (4) patients with diabetes history or blood glucose detection abnormal (fasting blood glucose $\geq 7\text{ mmol/L}$); (5) liver, renal function is abnormal (AST, Alt ≥ 1.5 times ULN, creatinine ≥ 1.5 times ULN); (6) has serious endocrine and metabolic diseases; (7) There are historical history of three high blood pressure; (8) History of osteoporosis; (9) History of autoimmune diseases; (10) Because of malignant tumors or other serious medical history, surgery should not be accepted or led to observation of teeth; (11) Pregnancy or lactating women; (12) Patients with anesthetic allergy; (13) Clinical or radiology shows that there are acute infections, root lesions, roots, severe eradications, dental bone rats, non-easy to abrasive, and osteoplasses (CEJ) or There is no treatment of untreated bilrels in the roots, the repair body is gains and / or in CEJ or the following repair edges are not in close; (14) A subject that can cause oral imaging inspection artifacts, such as: The study of teeth and its neighboring teeth are metal dentures, porcelain teeth; (15) a patient with root-stricken lesions;

3. Diagnostic criteria

(1) . Periodontal pocket $> 3\text{ mm}$, and inflammation, gingival bleeding (2) . Adjacent clinical attachment loss $> 1\text{ mm}$ (3) . Periodontal pocket bleeding on probing (4) . Alveolar bone has horizontal or vertical resorption. The progress of the disease is slow, and the teeth are loosened or displaced in the late stage.

4. Criteria for withdrawing / terminating tests

(1) . Any unexpected time to break blindness (2) . Patients who were found to be sensitive to or rejected implants during / after operation. (3) . Problems in need of treatment that met the exclusion criteria. (4) . Patients with irresistible factors such as non-migration / death lost follow-up during the study period.

VI. Research methods

1. Randomized controlled scheme

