CAL (clinical attachment level) : The distance from periodontal pocket bottom to CEJ was measured by periodontal probe (mm). Record six sites of each tooth (the mesial, median and distal site of the buccal and tongue surface).

mobility: use a tweezer to clamp the incisal areas of the anterior teeth or the pit groove on the occlusal surface of the posterior teeth and shake the teeth faciolingually, mesiodistally and vertically. I degree : abnormal mobility faciolingually or less than 1mm positioning. II degree : abnormal mobility faciolingually and mesiodistally or loosening range of 1-2mm. III degree : abnormal mobility faciolingually, mesiodistally and vertically or loosening range is

greater than 2mm.

BOP(bleeding of probe) : observe for 10-15 seconds after probe to see whether it bleeds. Record six sites of each tooth (the mesial, median and distal site of the buccal and tongue surface).

RBL(radiographic bone level): Locate the reference point at the deepest PD site of the affected tooth: cemento-enamel junction (CEJ), alveolar crest (AC), bone defect (BD) .RBL is the straight line distance from CEJ to BD (mm)

IC: IC is the straight line distance from AC to BD (mm)

regenerated bone volume parameters : in mimics software, threshold was set according to the gray value of the affected tooth and its surrounding alveolar bone, image editing and region growth were used to form a mask of the three-dimensional reconstruction area. The three-dimensional calculation function was used to reconstruct the three-dimensional shape of the alveolar bone in the target area. Furthermore, the structure of alveolar bone was optimized by remeshing and smooth. The volume of alveolar bone before and after operation was calculated by Boolean operation to obtain the model of regenerated alveolar bone and its volume was measured.

Defect fill (%) = (preoperative IC- and postoperative IC) / preoperative IC × 100%

Defect resolution (%) = (preoperative RBL- and postoperative RBL) / preoperative RBL × 100%

VIII. Statistical analysis method (statistical software: SPSS25.0)

1) data description: measurement data are described by mean \pm standard

deviation, non-normal distribution data are described by median and percentage (25th 75th percentile)

(2) baseline data are compared with normal distribution by one-way ANOVA test, while measurement data of non-normal distribution are described by Wilcoxon rank sum test.

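### Defect resolution (%) divides by the whole CEJ-to-base distance, so when the crest lies apical to the CEJ a completely filled defect scores below 100%, by an amount fixed before surgery

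*Combined protocol and SAP*

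**What the plan says.** Section VII (Observation index and evaluation of curative effect) names three landmarks: "Locate the reference point at the deepest PD site of the affected tooth: cemento-enamel junction (CEJ), alveolar crest (AC), bone defect (BD". It builds two distances on them: "RBL is the straight line distance from CEJ to BD (mm" and "IC is the straight line distance from AC to BD (mm". Each distance then gets a percentage index: "Defect fill (%) = (preoperative IC- and postoperative IC) / preoperative IC × 100" and "Defect resolution (%) = (preoperative RBL- and postoperative RBL) / preoperative RBL × 100". In both formulas the hyphen is read as a minus sign.

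Inclusion criterion 2 in section V asks that "imaging evaluation of the vertical bone absorption of the teeth is greater than 3 mm". The diagnostic criteria in the same section state: "Alveolar bone has horizontal or vertical resorption". No limit is set on the distance from CEJ to crest.

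Section VIII compares the groups by one-way ANOVA or a rank-based test, without covariates. No index is named as primary. Section VI.1 puts 26 patients in each of three groups.

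**The concern.** The surgery in section VI.3 packs graft into the intraosseous defect, the part between crest and base. An index called defect resolution should tell a reader how much of that part has gone. The formula instead expresses the change as a share of a longer distance, which also contains the bone already lost between CEJ and crest.

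Two patients with the same complete fill can therefore get different scores because of their anatomy before surgery. A reader who sees 50% would take the defect to be half resolved when it may be full. In the comparison of arms, variation in CEJ-to-crest distance enters the outcome as noise, and the planned unadjusted tests do nothing to remove it.

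**Working it through.** The plan gives a formula and no numerical result for this index, so there is no figure to reproduce. The check is algebra on the plan's own definitions.

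**Inputs**
- RBL = CEJ to BD, and IC = AC to BD (section VII).
- Depth: vertical resorption above 3 mm (section V, inclusion criterion 2). The values 3, 4 and 6 mm are used as examples.
- c = CEJ-to-crest distance. The documents do not give it; 1 to 6 mm is assumed.
- Landmarks are first taken as collinear, then as oblique.

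**Complete fill under the present formula.** With collinear landmarks, preoperative RBL = c + IC. Fill to the baseline crest leaves postoperative RBL = c. The score is (c + IC − c)/(c + IC) = IC/(IC + c).

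| Preoperative IC | c = 1 mm | c = 2 mm | c = 4 mm | c = 6 mm |
|---|---|---|---|---|
| 3 mm | 75.0% | 60.0% | 42.9% | 33.3% |
| 4 mm | 80.0% | 66.7% | 50.0% | 40.0% |
| 6 mm | 85.7% | 75.0% | 60.0% | 50.0% |

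For IC = 4 mm the arithmetic is 4/5, 4/6, 4/8 and 4/10. Defect fill is 100% in every cell. Defect resolution reaches 100% only if c = 0.

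**Ranking.** A completely filled 4 mm defect with c = 6 mm scores 4/10 = 40%. A 60%-filled 4 mm defect with c = 1 mm scores 2.4/5 = 48%. The worse result ranks higher.

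**Spread.** If depth is uniform on 3–6 mm, c is uniform on 1–6 mm and every defect is completely filled, simulated scores have mean 57.7%, SD 11.8 points and 5th–95th percentile 40.0–78.5%. With c confined to 1–3 mm, the mean is 69% and the SD 7.5 points.

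**Oblique wall.** Suppose AC lies off the root at angle θ. Fill to crest level then changes RBL by IC·cos θ, and the present score is IC·cos θ/(c + IC·cos θ). For IC = 4 mm, θ from 20 to 45 degrees and c from 1 to 4 mm, it runs from 79.0% down to 41.4%. The conclusion does not depend on collinearity.

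**With preoperative IC as denominator.** Complete fill gives IC/IC = 100% and half fill gives 50%, for every c, when landmarks are collinear. With an oblique wall, complete fill gives cos θ: about 94%, 87% or 71% at 20, 30 or 45 degrees.

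**Precision (illustration only).** Assume mean fill of 60% against 70%, SD 15 points, depth and c distributed as above, and a two-group t-test with 26 per arm. Simulated power is about 41–42% for the present ratio, 43% for unadjusted RBL change in mm, and 65–66% with preoperative IC as denominator. With oblique walls of 15–45 degrees, power rises from 37% for the present ratio to 59% with the IC denominator.

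**The case against.** The strongest reply is that the formula is a coherent relative change in radiographic bone level, and that nothing in the documents says 100% must mean filled to the crest. That stands, and it is why this is a fault of definition and label and not of arithmetic. The label still promises something the ratio does not deliver.

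Second, Defect fill is defined alongside and reads 100% when the intraosseous component has gone; RBL and IC in mm and bone volume are collected too. That limits the damage but does not remove it. Defect fill is measured from the crest, so crest loss counts as fill. If the crest drops 1 mm with no gain at the base, IC goes from 4 to 3 mm and Defect fill is 25%, while RBL shows no change. Defect resolution is the only percentage index tied to the CEJ.

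Third, the same formula applies to all arms. A reader might infer that the index biases the comparison of treatments. The documents do not support that: allocation is randomised, so c is balanced in expectation. What remains is extra variance and chance imbalance with 26 per arm.

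Fourth, it is tempting to say that switching to RBL change in mm solves the problem. It corrects the scale and the label, but unadjusted it gains almost no precision. With complete fill under the assumed ranges, the coefficient of variation is 19.2%, against 20.5% for the present ratio, because change in mm varies with initial depth.

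**Conclusion.** The concern holds at moderate severity, as an error in the definition of one index. Where the crest lies apical to the CEJ, complete fill to the baseline crest scores about IC/(IC + c), so each patient's ceiling is set by bone loss present before surgery. For a 4 mm defect that ceiling is 80% to 40% as c goes from 1 to 6 mm.

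The direction follows from the plan's own definitions. The size rests on assumed values of c and depth, and the exact figures on collinear landmarks.

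A reader might also infer that 100% can never be reached. That goes too far: the ceiling needs c > 0, which the documents make plausible by treating CEJ and crest as separate landmarks and listing horizontal resorption, but do not state for every patient. Bone regained above the baseline crest would also raise the score. Nor do the documents make this the trial's deciding outcome, since no index is named as primary.

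**What to change.** In section VII, define Defect resolution (%) = (preoperative RBL − postoperative RBL) / preoperative IC at the same site × 100%.

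Add a sentence stating that IC is measured directly from AC to BD, so with an oblique wall complete fill reads somewhat under 100%, unless the vertical component of IC along the root is used as denominator. The defect angle is already among the CBCT measurements in section VI.3.

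If the present ratio is kept, report it as *percent reduction in CEJ-to-base distance* and do not call it resolution. If RBL change in mm is analysed, adjust for baseline IC and RBL in section VIII, since the change scales with initial depth.

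The cost is one formula line and one explanatory sentence. IC and RBL are already measured at V0, V2 and V3, so no new data are needed. The downside is that the percentages will not be comparable with reports that use the RBL denominator.

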The newly diagnosed patients were recalled after 6-8 weeks of basic treatment to evaluate whether they met the inclusion exclusion criteria and confirm the operation site. For the patients considering inclusion, they agreed on the operation time one week later (female patients avoided menstruation). Oral health education was given to the patients again. One week later, the operative (V0), the informed consent form was signed by the patient, and then the researchers measured the baseline of the included patients, including (1) clinical periodontal index: probing depth (PD), clinical attachment level (CAL), mobility

(mobility), probing bleeding (BOP). (2) Imaging examination: the height of bone defect (IC), bone level (RBL) and the angle of intraosseous defect were measured by CBCT image, and the volume of intraosseous defect was measured after three-dimensional reconstruction of the affected teeth: all measurements were repeated twice to take the average value; before the actual measurement, all measurement researchers have passed the consistency test. Researcher A uses a random number table for random grouping and uses opaque sealed envelopes for distribution and concealment, and then hands over the envelopes to researcher B and no longer participates in the follow-up study. Researcher B numbered the enrolled patients 1-78 in order. Before the operation, researcher B handed over the sealed envelope to the itinerant nurse to open it, and both the patient and the patient were blind at this time. Since then, researcher B is responsible for supervising the operation. All the operations were performed by experienced surgeons. The surgical area was anesthetized before operation, intraoral and perioral routine disinfection was performed, and the operation was carried out in accordance with the principles of routine periodontal regeneration and aseptic operation.

If the patient was assigned to the APRF+GTR group, 20ml was collected with a blood collection needle from the superficial elbow vein immediately before operation and placed in two special glass centrifuges for APRF. Immediately after the blood collection was completed, the blood was symmetrically placed in the TR-18plu series centrifuge, and the 14min was centrifuged with 1500rpm at room

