was completed, the symmetrical Medifuge centrifuge was selected, and the CGF procedure was selected and centrifuged for 13 minutes. The CGF centrifugation procedure is as follows: accelerate for 30 seconds, rise to 2700r/min, centrifuge for 2 minutes, then descend to 2400r/min, centrifuge for 4 minutes, accelerate to 2700r/min, centrifuge for 4 minutes, then descend to 3000r/min, centrifuge for 3 minutes, and decelerate to stop in the last 36 seconds. Finally, the blood in the test tube is divided into three layers: the top layer is PPP, the lowest layer is crimson jelly-like red blood cells and platelets, and the middle layer is yellow translucent gel-like CGF. The 2 test tubes completed by centrifugation were placed vertically on the operating compartment table for backup (not tilted or inverted). The APRF gel in the above process was changed to CGF gel, mixed and covered with CGF, and the other operations were the same.

If the patient was assigned to the GTR group, no blood was drawn. Gel or membrane containing growth factor was not used to cover the operation, and the rest of the operation was the same.

At the end of the operation, the surgeon gave the patient postoperative medical advice and given postoperative medication: cefuroxime axetil 50mg, ornidazole 500mg, twice a day for 5-7 days. Oral hygiene education was given to the patients again, and patients were advised to use Koutai mouthwash twice a day for 2 weeks, and about 2 weeks later to remove stitches. Two weeks after operation, stitches were removed by the original surgeon, and the patients were scheduled for 12 weeks \pm 7 days (V1), 24 weeks \pm 14 days (V2) and 48 weeks \pm 28

days (V3).

VII. Observation index and evaluation of curative effect

The patients were contacted and followed up by researcher B at 12, 24 and 48 weeks after operation. At 12 weeks \pm 7 days after operation, PD, CAL, mobility and BOP were measured by measurement researchers. 24 weeks \pm 14 days and 48 weeks \pm 28 days after operation, the researchers measured PD, CAL, mobility, BOP, RBL, IC, intraosseous defect angle and bone defect volume.

PD (probe depth) :use a periodontal probe (UNC-15,Hu-Friedy,Chicago,IL) paralleling to the long axis of the tooth to measure the distance from the bottom of the periodontal pocket to the gingival margin (mm), record six sites of each tooth (the mesial, median and distal site of the buccal and tongue surface).

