(3) to compare the curative effect, first of all, the normality and homogeneity of variance of the experimental data were tested. If it obeys normality and homogeneity of variance, one-way analysis of variance (One-Way ANOVA) is used to compare the differences of mean among groups. If there were significant differences, pairwise comparisons were made, and multiple comparisons were made with SNK-q test to analyze and compare the differences between groups. If it does not obey normality and homogeneity of variance, Friedman test is used to compare the mean difference of each group; if there is significant difference, pairwise comparison is made by Wilcoxon Matched-Pairs Sighed Rank test. $P < 0.05$ was used as an index of statistical difference.

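### The ANOVA for efficacy ignores the baseline value of six continuous outcomes measured before surgery; the precision lost runs from none to large, depending on how well baseline predicts outcome.

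*Combined protocol and SAP*

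**What the plan says.** Section VIII, item (3), first requires that "the normality and homogeneity of variance of the experimental data were tested". If both hold, "one-way analysis of variance (One-Way ANOVA) is used to compare the differences of mean among groups", and after a significant result "multiple comparisons were made with SNK-q test". No covariate is named here or anywhere else in the document.

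Six continuous outcomes have a V0 value. Section VI.3 lists PD and CAL among the clinical measures, states that "the height of bone defect (IC), bone level (RBL) and the angle of intraosseous defect were measured by CBCT image", and adds defect volume from the three-dimensional reconstruction. Section VII repeats PD and CAL at 12 weeks. At 24 and 48 weeks, "the researchers measured PD, CAL, mobility, BOP, RBL, IC, intraosseous defect angle and bone defect volume". Mobility is graded and BOP is yes/no, so neither is counted.

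Baseline enters in only two other ways. Section VIII, item (2), says that "baseline data are compared with normal distribution by one-way ANOVA test". Section VII defines measures relative to the preoperative state: regenerated bone volume, defect resolution, and "Defect fill (%) = (preoperative IC- and postoperative IC) / preoperative IC", expressed as a percentage. Item (3) does not list the outcomes it covers or say whether follow-up values or changes are analysed.

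**The concern.** In a randomised trial, a one-way ANOVA on follow-up values or on changes is valid. The worry is wasted information. If baseline predicts follow-up, analysing follow-up values leaves that predictable variation in the error term. If baseline predicts follow-up poorly, subtracting it adds noise. The plan leaves the choice open, and each option is inefficient over part of the range.

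There are 26 patients per arm and no stratification on baseline defect is stated, so a chance baseline difference also carries into the estimated treatment difference. A between-arm test of baseline adjusts nothing. The documents give no power calculation, so nothing shows that the trial can afford the loss.

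This point covers the ANOVA branch only. The Friedman and matched-pairs Wilcoxon branch is for related samples, is not cleared by anything here, and needs separate repair.

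**Working it through.** **Inputs from the documents.** Three arms of 26 and significance at P < 0.05 (sections VI.1 and VIII). 3 × 26 = 78 agrees with the stated total. The sample size cannot be reproduced further, because no effect size, SD, power or dropout rate is given.

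**Assumptions not in the documents.** Baseline/follow-up correlation ρ; arm means (0, d, d) with d = 0.7 SD; equal baseline and follow-up SDs (this matters only for the change-score figures).

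**Error variance, in units of the follow-up variance.** Follow-up value: 1. Change score: 2(1 − ρ). ANCOVA: 1 − ρ².

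**Three-group power.** The overall mean is 2d/3, so the squared deviations sum to (4/9 + 1/9 + 1/9)d² = 2d²/3. The noncentrality is 26 × (2/3) × 0.49 / variance = 8.49 / variance. Error degrees of freedom are 75 for ANOVA and 74 for ANCOVA.

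| ρ | Follow-up ANOVA | Change-score ANOVA | ANCOVA |
|---|---|---|---|
| 0 | 72.7% | 42.3% | 72.6% |
| 0.1 | 72.7% | 46.3% | 73.1% |
| 0.2 | 72.7% | 51.2% | 74.5% |
| 0.3 | 72.7% | 57.1% | 76.9% |
| 0.5 | 72.7% | 72.7% | 84.8% |
| 0.7 | 72.7% | 92.0% | 95.7% |

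A simulation that includes the cost of estimating the slope (30,000 trials per ρ) gave 72.2%, 72.9%, 73.6%, 76.0%, 84.4% and 95.4% for ANCOVA. In simulation, ANCOVA is about 0.7 points behind follow-up ANOVA at ρ = 0.

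**95% CI half-width for one pairwise difference** = t × √(2/26 × variance). For follow-up values, 1.99 × 0.277 = 0.55 SD. At ρ = 0.2, 0.3, 0.5 and 0.7, change scores give 0.70, 0.65, 0.55 and 0.43 SD; ANCOVA gives 0.54, 0.53, 0.48 and 0.39 SD.

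**Effect of the inclusion floor on ρ.** Section V.1 requires that "imaging evaluation of the vertical bone absorption of the teeth is greater than 3 mm osteogenesis". If baseline defect depth is taken as normal (mean 5, SD 1.5 mm) and cut at 3 mm, ρ of 0.3, 0.5 and 0.7 becomes 0.26, 0.44 and 0.64.

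**Chance imbalance.** In 400,000 draws of three arm means, the largest baseline gap exceeded 0.4 SD in 31.8% of randomisations. The planned baseline ANOVA did not flag 84.3% of those. For one named pair, the standard error is √(2/26) = 0.277 SD and 0.4/0.277 = 1.44, so about 15% exceed 0.4 SD. A 0.4 SD gap shifts an unadjusted follow-up difference by 0.4ρ: 0.08, 0.12, 0.20 and 0.28 SD at ρ = 0.2, 0.3, 0.5 and 0.7. It shifts a change-score difference the other way by 0.4(1 − ρ): 0.32, 0.28, 0.20 and 0.12 SD.

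**Percent defect fill.** Simulation used the same assumed depth distribution, a mean reduction of 2 mm with GTR alone, and 4,000 trials per ρ. At ρ = 0.2, 0.3, 0.5 and 0.7, power without the covariate was 69.1%, 71.4%, 82.8% and 93.3%; with baseline IC added it was 72.3%, 73.3%, 82.3% and 94.0%. The change is about −0.5 to +3 points, so no gain is claimed for this measure.

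**The case against.** The strongest reply is that this is an efficiency point whose size rests on an unknown correlation. That is right: only the absence of the covariate is certain. Against follow-up ANOVA the gain is under 2 points at ρ of 0.2 or less and about 4 points at 0.3. For PD the position may be weaker still, because section V.1 also requires a site of at least 5 mm. With baseline PD assumed normal (SD 1.5 mm, mean 5.5 to 6.5 mm) and cut at 5 mm, ρ of 0.5 falls to between 0.36 and 0.42. That stays inside the range tabulated above, where adjustment still helps.

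The change-score figures do depend on equal SDs. At ρ = 0.5, power is 60% or 80%, not 73%, if the follow-up SD is 0.8 or 1.25 times the baseline SD. Both remain below the 85% for ANCOVA.

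It can also be said that fill, resolution and regenerated volume already contain baseline. They do, but a ratio or difference is not covariate adjustment, and none of them covers PD, CAL or defect angle. Of the three, only percent fill was simulated.

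Finally, the remedy reaches past the ANOVA itself, since it drops the pre-test routing and SNK-q for these outcomes. That is deliberate. Pairwise comparisons must use the adjusted means. The pre-tests would also divert sound data: with Shapiro-Wilk in each arm or Levene at 0.05 (assumed, as the plan names no tests), 18% of truly normal, equal-variance trials were routed away from ANOVA (6,000 trials).

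**Conclusion.** The concern holds. Six continuous outcomes have a baseline value that the ANOVA branch does not use as a covariate. The analysis is valid but may be inefficient. On the assumptions shown, the loss against ANCOVA is from nil to 23 points of power if follow-up values are analysed (ρ 0 to 0.7), and from 30 points down to 4 if changes are analysed. The true size cannot be fixed from the documents.

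The sponsor need not know ρ to decide. Apart from under one point near ρ = 0, ANCOVA is at least as powerful as either unadjusted option throughout the range shown. The change should be made, though the trial's validity does not depend on it.

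**What to change.** For PD, CAL, IC, RBL, defect angle and defect volume, prespecify ANCOVA of the follow-up value on treatment group, with that outcome's own V0 value as covariate. Apply it at 12 weeks for PD and CAL and at 24 and 48 weeks for all six. For PD and CAL, state in advance one site or one summary of the six sites, and use it at both baseline and follow-up.

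Use this as the efficacy analysis for these outcomes without first routing them by the normality and variance tests. After a significant three-group test, compare adjusted means pairwise by t contrasts from the same model in place of SNK-q, and report adjusted differences with 95% CIs. In simulation (60,000 trials per setting), this sequence gave any false pairwise claim in 4.8% to 5.0% of trials under the complete null. When both adjunct arms were equally better than GTR, APRF and CGF were falsely declared different in 4.9% to 5.1%.

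Prespecify HC3 robust standard errors as a sensitivity check. If one arm's SD is twice the others', ANCOVA rejects in 6.1% to 6.7% of null trials, HC3 in 4.7% to 5.6%, and unadjusted ANOVA in 5.4% to 6.6%.

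The cost is SAP wording and one degree of freedom per model, with about 0.7 points of power lost if baseline predicts nothing. No new data are needed. The change does not settle which of these outcomes and visits is primary.

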A simple random method is used for random grouping. The specific method is as follows: first, a column number 1x 78 is established by Excel2013, and then the random number between 0 and 1 is generated by the other column, and then sorted by the largest to the smallest. The first 26 numbers are assigned to the GTR group, the middle 26 numbers are assigned to the APRF+GTR group, and the last 26 numbers are assigned to the CGF+GTR group. The subjects were divided into GTR group, APRF+GTR group and CGF+GTR group according to 1:1:1. (2) researcher A put the implant name (APRF or CGF or none) corresponding to the group mark into 78 Kraft paper envelopes with serial number 1: 78 and opaque according to the distribution order list. A gave the sealed envelope to B and no longer participated in the follow-up study. Researcher B is responsible for including the subjects according to the inclusion criteria, assigning the tested according to the order of seeing a doctor, and is responsible for supervising the operation process.

2. Blind design

Researcher A put the name of the implant corresponding to the group mark (APRF or CGF or none) into 78 Kraft paper envelopes with serial number 1x78 and opaque according to the assigned order list. A gave the sealed envelope to B and no longer participated in the follow-up study. Researcher B is responsible for including the subjects according to the inclusion criteria and assigning the number of the subjects according to the order of seeing a doctor. During the operation, researcher B will hand over the sealed envelope to the surgeon according to the number, supervise the operation process, and do not participate in other studies such as measurement. The survey researcher is responsible for measuring various indicators on a regular basis. Until the end of the experiment, the measurement researchers did not know how the subjects were grouped.

3. Treatment scheme

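### The one-way ANOVA in section VIII(3) uses one value per patient and leaves baseline and other-visit data unused, so a patient without a 48-week value adds nothing to the 48-week comparison

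*Combined protocol and SAP*

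**What the plan says.** Section VIII(3) gives the efficacy analysis. If normality and equal variance hold, "one-way analysis of variance (One-Way ANOVA) is used to compare the differences of mean among groups", followed by SNK-q pairwise comparisons. If they do not, "Friedman test is used to compare the mean difference of each group", followed by Wilcoxon matched-pairs tests. No longitudinal model, baseline covariate, imputation rule, analysis set, primary outcome or primary visit is named.

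The data collected are richer than that analysis uses. Section VII says "The patients were contacted and followed up by researcher B at 12, 24 and 48 weeks after operation". At 12 weeks, "PD, CAL, mobility and BOP were measured by measurement researchers", with no imaging. At 24 and 48 weeks the clinical measures are repeated, and bone level, defect height, defect angle and defect volume are added. Section VI.3 takes a baseline for all of these.

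Section V.4(4) lists patients "lost follow-up during the study period" among the withdrawals. It does not say how their data are handled.

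**The concern.** A one-way ANOVA takes one value per patient and omits anyone who has none. A patient seen at 12 and 24 weeks but not at 48 drops out of the 48-week comparison, although their earlier values say something about where they would have been. Two things are at stake.

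- **Precision.** In a trial of 26 per arm, information already paid for is not used. This applies to the earlier visits when someone is lost, and to the baseline value for everyone.
- **Bias.** If patients who left one arm differed in their 24-week result from those who stayed, a comparison of attenders would be shifted. A model that uses the 24-week value could correct for that.

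The fallback for non-normal data does not help, because the Friedman and matched-pairs tests need complete blocks or pairs.

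**Working it through.** **The plan's own figure.** Allocation: "each random group is allocated according to the proportion of 1:1:1". Group size: "The first 26 numbers are assigned to the GTR group", and likewise for the other two groups. 3 × 26 = 78, which agrees with section VI.1. The documents give no effect size, SD, power or dropout rate, so 78 itself cannot be reproduced. As a yardstick, 26 per arm gives 80% power for a single pairwise comparison (two-sided 0.05 assumed) at a difference of (1.960 + 0.842) × √(2/26) = 0.777 SD.

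**Assumed inputs (not in the documents).** Proportion missing at 48 weeks but seen at 24 weeks: d = 10% to 20% in each arm. Correlation of the 24- and 48-week values: ρ = 0.3 to 0.8.

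**Step 1: precision from the 24-week value.** Relative to complete data, the variance of a 48-week mean is:
- attenders only: 1/(1 − d)
- likelihood-based model using 24 weeks: 1 + [d/(1 − d)] × (1 − ρ²)

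The ratio of the second to the first is 1 − dρ², so the variance falls by dρ². The effective number per arm is 26(1 − d)/(1 − dρ²). Power is at 0.777 SD.

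| d | ρ | variance reduction | effective n (attenders → model) | power (attenders → model) |
|---|---|---|---|---|
| 10% | 0.3 | 0.9% | 23.4 → 23.6 | 75.7% → 76.1% |
| 10% | 0.5 | 2.5% | 23.4 → 24.0 | 75.7% → 76.8% |
| 10% | 0.7 | 4.9% | 23.4 → 24.6 | 75.7% → 77.8% |
| 10% | 0.8 | 6.4% | 23.4 → 25.0 | 75.7% → 78.4% |
| 20% | 0.3 | 1.8% | 20.8 → 21.2 | 70.7% → 71.5% |
| 20% | 0.5 | 5.0% | 20.8 → 21.9 | 70.7% → 72.9% |
| 20% | 0.7 | 9.8% | 20.8 → 23.1 | 70.7% → 75.1% |
| 20% | 0.8 | 12.8% | 20.8 → 23.9 | 70.7% → 76.5% |

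**Step 2: bias if loss in one arm depends on the 24-week value.** Assume standard normal outcomes, loss in one arm logistic in the 24-week value, and any loss in the other arm unrelated to outcome. The bias of the attenders-only 48-week mean is ρ × (mean 24-week value among those who stay). By numerical integration:

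| log-odds per SD | missing | mean 24-week value of stayers | bias, ρ = 0.6 | bias, ρ = 0.8 |
|---|---|---|---|---|
| 0.5 | 10% | 0.049 SD | 0.029 | 0.039 |
| 0.5 | 20% | 0.096 SD | 0.058 | 0.077 |
| 1.0 | 10% | 0.091 SD | 0.054 | 0.073 |
| 1.0 | 20% | 0.173 SD | 0.104 | 0.139 |

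The range is 0.03 to 0.14 SD. With 20% lost in one arm and none in the other, the standard error of the difference is √(1/20.8 + 1/26) = 0.29 SD, so the largest of these biases is about half a standard error. Regression on the 24-week value brings the bias to about 0 here, but by construction: loss was made to depend on that value alone.

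**Step 3: baseline adjustment, with or without dropout.** With baseline-to-follow-up correlation r (assumed 0.3, 0.5, 0.7), adjusting for baseline multiplies the variance of raw follow-up values by 1 − r²: 0.91, 0.75, 0.51. The equivalent n per arm is 26/(1 − r²): 28.6, 34.7, 51.0. If change scores were analysed instead (the plan does not say), with equal SDs, the factor against them is (1 − r²)/[2(1 − r)] = (1 + r)/2: 0.65, 0.75, 0.85. Steps 1 and 3 do not simply add. Once baseline is in the model, the correlation in step 1 becomes the partial correlation given baseline.

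**The case against.** The strongest reply is that a one-way comparison at each visit is a valid and simple method for a 78-patient trial. That stands: this is a loss of efficiency, not an error. Several stronger readings are tempting, and the documents do not support them.

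- **That such patients are removed altogether.** A reader might infer this from section V.4. That section concerns withdrawal from the trial, and section VIII defines no analysis set. A patient missing at 48 weeks still counts at visits attended. That each visit is tested separately on attenders is itself an inference from the method named.
- **That a completers-only 48-week analysis was chosen as primary.** No primary visit is named; 48 weeks is simply the last.
- **That poor responders will leave one arm.** V.4(4), though garbled, ties loss to unavoidable circumstances such as death, not to poor results. The bias figures show what could happen, not what is expected.
- **That the bias is large.** Reaching 0.16 to 0.21 SD (ρ 0.6 to 0.8) takes about 24% missing in one arm and log-odds of about 1.5 per SD, and nothing in the documents points there.
- **That earlier data always help.** There is no 12-week imaging, so for bone outcomes the 24-week value helps only for patients seen at 24 weeks.

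It is also fair to say that baseline is not wholly ignored. The defect-fill and defect-resolution percentages in section VII are built from preoperative values. The efficacy test still has no baseline term.

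Using matched-sample tests on independent arms in the non-normal branch is a separate matter that this point does not resolve.

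**Conclusion.** The point holds as an optional improvement. The planned test leaves baseline and other-visit values unused, and a patient without a 48-week value adds nothing to that comparison.

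The gain from the 24-week value is modest: about 1% to 13% of the variance, or roughly 0.4 to 6 points of power at the reference difference. The possible bias is about 0.03 to 0.14 SD, and only if loss in one arm depends on the 24-week result. The model removes it only if data are missing at random given the observed values.

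With no dropout, only the baseline-adjustment gain remains. That may be the larger benefit, at 9% to 49% of the variance of raw follow-up values for r of 0.3 to 0.7. Dropout, correlations and the loss mechanism are all assumptions.

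**What to change.** In section VIII(3), for continuous outcomes measured at baseline and follow-up, replace the one-way ANOVA with a linear mixed model. Its terms are arm, visit, arm-by-visit, baseline value and baseline-by-visit, with unstructured covariance over visits. Include all randomised patients with any post-baseline value. Visits are 12, 24 and 48 weeks for clinical measures, and 24 and 48 weeks for imaging. Report the 48-week pairwise differences with 95% confidence intervals. Mobility grade and bleeding on probing are not continuous and need their own method.

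Because the model relies on data being missing at random, also report by arm how many patients have no post-baseline value, and name one sensitivity analysis for data not missing at random.

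The cost is SAP wording, settled before group codes are known. No visit or measurement is added, and the MIXED procedure in the named SPSS 25 fits the model. The downside is that a covariance structure must be specified and the output is less simple than an ANOVA table.
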